## 4.5 Replacement of participants

In total, 150 evaluable participants will be included and exposed to IMP. If a participant/legal guardian withdraws his/ her consent prior to IMP dosing, he/ she will be replaced. If a participant is withdrawn due to technical reasons or due to a surgical unrelated medical complication, he/ she will be replaced.

Rescreening of participants will not be allowed.

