## PROTOCOL OUTLINE

Title of Study & Design	PDC 01-0202: Open-label, prospective study to assess the safety, tolerability, analgesic effect, and feasibility of IN SUF/KET in pediatric patients with moderate or severe pain, in an acute care setting
Study population	Pediatric participants from 1 year to <18 years inclusive. The aim will be to recruit the following minimum participants per age group: Age 1 - <5 years: 20 participants Age 5 - <9 years: 40 participants Age 9 - <18 years : 40 participants The remaining participants can be flexible enrolled.
Number of patients	150 pediatric participants evaluable for the primary endpoint
Investigators/ Study Sites	The study will be conducted at multiple sites in the Europe
Diagnosis and Main Criteria for Inclusion	
Key inclusion criteria:
 
 
- Pediatric participant, age 1 year to <18 years
 
- Attending an Emergency Department (ED) following an injury
 
- Acute pain of moderate or severe intensity (corresponding to 5 or above on an age-appropriate pain scale (0-10 NRS, Wong-Baker FACES scale and FLACC pain scale)
 
- Obtained informed consent by parent/guardian and assent from the child if possible and relevant (age dependent)
 
 
Key exclusion criteria:
 
 
- Participant showing abnormal nasal cavity/airway such as: 
 
- major septal deviation
 
- evidence of previous nasal disease or surgery
 
- current significant nasal congestion due to common cold
 
 
 
- Has received treatment with sufentanil and/or ketamine during the last 72 hours
 
- Known or suspected allergy to ketamine or sufentanil
 
- Critical, life- or limb-threatening condition requiring immediate management
 

Test Product, Dose and Mode of administration	
[REDACTED]
 
[REDACTED]
 
[REDACTED]
 
The dose may be repeated once after 10-15 min in case sufficient analgesia is not achieved after the first dose (i.e. pain intensity score >4/10 on age-appropriate pain scale per PI discretion).

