### 4.4 Participant Withdrawal

The Investigator will explain to the participant and legal guardian that they have the right to withdraw from the study at any time, and that this will not prejudice any future treatment. A participant who has consented to the study but not yet received IMP will be considered a screen failure if they decide to withdraw consent prior to receiving IMP. Once a participant has been administered IMP and subsequently decides to withdraw consent, the participant would be considered withdrawn. The reason for any kind of withdrawal must be recorded in the eCRF.

Reasons for withdrawing from may be:

- Unacceptable adverse events
- Participant or guardian's request
- Investigator's discretion
- Intercurrent illness

Whenever a participant is withdrawn from the study, the reason(s) of why the participant was withdrawn from the study should be recorded. All documentation concerning the participant must be as complete as possible, however, no new information can be collected if the participant or legal guardian has withdrawn his/her consent/assent to further study participation.

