### 7.1 Estimation of Sample Size

So far, data from 375 children on IN sufentanil/ketamine show a safe and tolerable combination (data from PDC 01-0201, PDC 01-0203 and PDC 01-0206). Thus, from a safety perspective it is expected that 150 patients will be sufficient to capture and confirm the adverse event profile of the IMP. Furthermore, a sample size calculation was made for the primary efficacy endpoint on the basis of expecting a responder rate of 60%. A previous study reported a responder rate of 71.6 %, defined as pain intensity  $\leq 3$  at 30 min post IMP (16). With a sample of 113 patients, a one-sample one-sided proportion design would provide at least 80% power to show that the responder rate is more than to 60%, with a significance level of 5%. Accounting for an approximate 25% dropout rate the resulting sample size is 150.

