#### Full Analysis Set (FAS)

The full analysis set (FAS) will consist of all participants who received at least one dose of study treatment. The FAS follows the intention-to-treat (ITT) principle, i.e. participants will be analysed, regardless of whether treatment was received as planned. The FAS will be used for the analysis of primary and secondary objectives.

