### 7.3 Method of imputation

The amount of missing data will be reported as appropriate, and no other imputation will be performed.

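### The plan does not say how a dosed child without a usable pain score counts in the primary responder rate, so a stated intention-to-treat rate can become a rate among scored children

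*Combined protocol and SAP*

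**What the plan says.** Section 7.2 defines the analysis set by dosing: "The full analysis set (FAS) will consist of all participants who received at least one dose of study treatment". It invokes the intention-to-treat principle, so that "participants will be analysed, regardless of whether treatment was received as planned", and uses this set for the primary objectives.

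Section 7.3 says that the amount of missing data will be reported and that "no other imputation will be performed". The synopsis differs. It promises a description of missing-data handling for each set of efficacy endpoints and rules out imputation only for safety endpoints. Section 7.4.1 reports a proportion with a 95% confidence interval and gives neither the denominator nor the status of a child without a score.

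The synopsis sets the target at "150 pediatric participants evaluable for the primary endpoint". Sections 4.1 and 4.5 also speak of 150 evaluable participants, and no section defines evaluable. Section 7.1 reaches the same number another way: "Accounting for an approximate 25% dropout rate the resulting sample size is 150".

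Section 4.5 has two replacement rules. The first is tied to the time before dosing: "If a participant/legal guardian withdraws his/ her consent prior to IMP dosing, he/ she will be replaced". The second is not: "If a participant is withdrawn due to technical reasons or due to a surgical unrelated medical complication, he/ she will be replaced". Section 4.4 calls a child whose consent is withdrawn before dosing a screen failure, and continues: "Once a participant has been administered IMP and subsequently decides to withdraw consent, the participant would be considered withdrawn".

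Section 4.3.7 leaves pain scores taken after rescue out of the efficacy analyses and defers the detail to the SAP.

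**The concern.** In a single-arm trial the responder rate is the whole efficacy result, so its denominator has to be fixed. Three groups of dosed children may have no usable score at 15 minutes or within 30 minutes: those who leave very early, those with a missed assessment, and those given rescue before the timepoint. If they drop out of the denominator, the rate describes children with scores and not all dosed children, which contradicts section 7.2. Rescue is given for insufficient pain relief, so at least that group is likely to contain non-responders, and leaving it out would push the rate up.

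The recruitment wording points the same way. A target of 150 evaluable children, with replacement of withdrawn children not limited to the time before dosing, suits an analysis of scored children better than an analysis of everyone dosed. The trial is open label, so whoever assigns a withdrawal to undefined technical reasons also knows how the child is doing.

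**Working it through.** **1. The plan's own sample size.** Inputs from section 7.1: reference rate p0 = 0.60, one-sided alpha 0.05, power at least 80%. The alternative is taken as p1 = 0.716, the previous study's rate; the text does not say so outright.

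- Normal approximation: n = [(z0.95·√(p0(1−p0)) + z0.80·√(p1(1−p1))) / (p1−p0)]² = 104.4.
- With continuity correction: (n/4)·[1 + √(1 + 2/(n(p1−p0)))]² = 112.9, so 113.
- Exact binomial at n = 113: 77 or more responders needed, alpha 0.046, power 0.822.
- Dropout: 113/0.75 = 150.7, against the stated 150.

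The sample size reproduces, and there is no arithmetic error. The 150 of section 7.1 is a total that already allows for 25% loss, whereas the synopsis and sections 4.1 and 4.5 treat 150 as the number evaluable. If 25% were lost after dosing, 150 evaluable would need 150/0.75 = 200 dosed, while section 4.1 expects 180 screened.

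**2. Effect of the denominator.** Inputs: 150 dosed, and about 71.6% response among scored children. The number unscored, m, is an assumption. Responders r = 0.716 × (150 − m), rounded. Observed-score rate = r/(150 − m). All-dosed rate with unscored children as non-responders = r/150. If every unscored child had responded, it would be (r + m)/150. Intervals are exact 95%.

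| m | Observed-score rate | Unscored as non-responders | Unscored as responders |
|---|---|---|---|
| 8 | 102/142 = 71.8% (63.7–79.1) | 102/150 = 68.0% (59.9–75.4) | 110/150 = 73.3% |
| 15 | 97/135 = 71.9% (63.5–79.2) | 97/150 = 64.7% (56.5–72.3) | 112/150 = 74.7% |

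The all-dosed rate falls to 60% when 0.716 × (1 − x) = 0.60, so x = 1 − 0.60/0.716 = 16.2% unscored.

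**3. Effect if recruitment is topped up to 150 scored children.** With 107/150 = 71.3% among scored children and k replaced children dosed but unscored, the all-dosed rate with those k as non-responders is 107/155 = 69.0% (k = 5) or 107/165 = 64.8% (k = 15). This gap exists only if the k children are left out of the denominator. If they are kept in, replacement has no effect of this kind.

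**The case against.** A reader might infer from section 4.5 that replaced children are removed from the analysis and that the primary rate is simply that of children who stayed. The documents do not say this. No section takes a replaced child out of the full analysis set, and no evaluable or per-protocol set exists. That the second replacement rule covers dosed children is a fair inference, since section 4.4 calls a consent withdrawal before dosing a screen failure, but it remains an inference. Section 6.1.1 defines the endpoint as the percentage of participants with a score of 4 or below; a child with no score has no such score and could already be counted as a non-responder. The text allows both readings.

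Nor does the second rule cover everyone who leaves. Adverse events, a participant's or guardian's request, and the investigator's discretion are withdrawal reasons in section 4.4, but section 4.5 does not name them as grounds for replacement.

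Sections 4.2 and 4.3.2 also require a pain score before premature withdrawal, and the 30-minute endpoint accepts any qualifying score in that window. Many early leavers can therefore be classified. This narrows the exposure mainly to the 15-minute endpoint, very early withdrawals and scores left out after rescue. It does not close the gap, because section 4.4 bars new data once consent is withdrawn.

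Finally, the separate SAP promised in section 7 may settle the matter; it is not part of the combined document. Section 7 requires it to be signed only before database lock, and in an open-label trial a rule written then may follow knowledge of the outcomes.

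**Conclusion.** The point stands as a gap in the denominator and missing-score rules, with the replacement rule as a contributing factor. Sections 7.2, 7.3 and 7.4.1 together do not determine the primary responder rate, and section 7 does not supply what the synopsis promises on missing efficacy data. The rate can become one among scored children and can then overstate response. Bias is possible, not shown.

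The size is bounded by assumption. With 150 dosed and all unscored children as non-responders, the rate drops by 3.8 percentage points with 8 unscored (71.8 − 68.0) and by 7.2 with 15 (71.9 − 64.7). These are upper bounds, and the documents give no expected number of unscored children.

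A reader might apply the full 25% dropout allowance and conclude that the result falls below 60%: 81/113 = 71.7% would become 81/150 = 54.0%. That requires the whole allowance to be post-dose, unscored non-responders, which nothing in the plan supports. It also illustrates missing data and not replacement, since nobody in it is replaced. The 60% is a reference in the sample-size rationale only; sections 7.4 and 7.4.1 make the analysis descriptive, and no success rule depends on it.

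**What to change.** - **Sections 7.3 and 7.4.1:** use all children in the full analysis set, including any who were replaced, as the denominator. For the 15-minute endpoint, count a child with no usable 15-minute score as a non-responder. For the 30-minute endpoint, count as a non-responder a child with no score of 4 or below before withdrawal or rescue within 30 minutes. Report the observed-score rate as a sensitivity result, with the number unscored and the reasons.
- **Section 4.5:** limit replacement to children who leave before any study drug is given, or state that replaced dosed children stay in the denominator. Define evaluable, and say whether 150 is the number dosed or the number with scores.
- **Synopsis and section 7.3:** align the two statements on missing efficacy data.
- **Timing:** name the dose from which 15 minutes is counted. Section 6.1.1 counts from the first dose, while section 4.3.2 restarts the schedule after a second, so without this the non-responder rule could catch children only because their schedule was reset.

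The cost is a few sentences and no new data. The reported rate may be slightly lower, and some true device failures will count against the product.

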## 5 INVESTIGATIONAL MEDICINAL PRODUCT

[REDACTED]	[REDACTED]
[REDACTED]	[REDACTED]

### 5.1.1 ■

[REDACTED]

[REDACTED]

[REDACTED]

[REDACTED]

[REDACTED]

[REDACTED]

The handling and storage will be further detailed in the IMP manual.

The IMP will be stored at room temperature (2-25 °C) at the study site in a secure area (a locked cabinet or drug storage room), protected from unintended use. A temperature log will be kept.

IMPs will be labelled according to local requirements.

### 5.1.2 Non-investigational medicinal products (NIMPs)

#### Rescue medication

Rescue medication can be given on the discretion of the investigator at any time in case of insufficient pain relief of IMP. Rescue medication should be given in accordance with local clinical practice. The type of rescue medication, dose and time of administration will be recorded in the eCRF.

## 5.2 Supply, Packaging, Labelling, Handling and Storage

The IMP will be manufactured, packaged, study labelled, batch certified by a qualified person (QP), and distributed in accordance with the principles of *Good Manufacturing Practice* and *Good Distribution Practice*, under the responsibility of Cessatech (or its designee).

IMP is prepared for dosing according to instructions. Detailed instructions for the preparation and handling of IMP will be provided by sponsor.

[figure not shown]
The wording on the participant-specific labels will be in accordance with *Good Manufacturing Practice* regarding labelling and national and/or local regulatory requirements.

## 5.3 Dosage and Administration

Dosing of CT001 in children is presented in mcg/kg (SUF) and mg/kg (KET). [REDACTED]

[REDACTED]  
[REDACTED]  
[REDACTED]  
[REDACTED]  
[REDACTED] to allow for simple dosing instructions while keeping an adequately narrow dose range around the target dose. This approach and the below dosing chart ([Table 2](#)) have been endorsed by the EMA.

The below dosing table described one dose administration, which then can be repeated once after 10-15 min, in the case of insufficient pain relief. Actuations should be given in alternating nostrils.

[REDACTED] The dose administration is also be described in a separate IMP manual.

## 5.4 Number of Participants Treated in Different Age Groups

Participants from 1 to <18 years of age (inclusive) will be enrolled into the study. The aim will be to enrol the following minimum number of participants in each age group:

- Age 1 - <5 years: 20 participants
- Age 5 - <9 years: 40 participants
- Age 9 - <18 years (inclusive): 40 participants

The remaining 50 participants can be flexibly enrolled into the age groups. Deviations to the above numbers may be accepted in case of recruitment challenges in some age groups.

## 5.5 IMP Accountability

All IMP for this study must be always retained in a safe place. Only personnel authorised by the PI at the site should dispense and administer the IMP. The investigator or pharmacist must complete an IMP accountability log, documenting product dispensed and used. This will be verified by the study monitor prior to destruction. Remaining IMP will be sent for destruction at the local hospital pharmacy, and this will be documented with a destruction certificate. If local pharmacy cannot destroy IMP, it can be returned for destruction according to the IMP manual.

## 6 RESPONSE VARIABLES AND ENDPOINTS

### 6.1 Assessment of Efficacy

#### 6.1.1 Primary efficacy variable

To investigate the analgesic efficacy of IN CT001 in pediatric participants in the acute care setting experiencing pain of moderate to severe intensity.

- Analgesic efficacy will be assessed as changes in pain intensity from baseline using age relevant scoring instruments (FLACC score for ages  $\geq 1$  year to  $< 5$  years, the Wong-Baker faces scale from ages  $\geq 5$  years to  $< 9$  years, and the 0-10 Numerical Rating Scale (NRS) from ages 9 and above). The pain assessments will be made prior to the first IMP dose (baseline) and then at the following timepoints: at 10, 15, 20, 30, 45, 60 min post first IMP dose. The primary efficacy endpoints will be the responder rate i.e., the percentage of participants that has a pain intensity score at 4 or below at 15 min and at any timepoint during 30 min post IMP.

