Duration of Treatment	Patients will receive a single dose of CT001, with the option of a second dose after 10-15 min where sufficient analgesia is not achieved after first dose. Efficacy, safety monitoring, including measurement of vital signs will continue for 60 min. after the last dose or until rescue medication or procedures are initiated.
Control(s)	None

Primary Objectives	Endpoints	Assessments
To assess the safety and tolerability of CT001 in pediatric participants with moderate to severe pain in an acute care setting	The number and proportion (%) of participants with AEs  Number of AEs, graded by severity, and number of SAEs.	Pulse rate, Respiratory rate Peripheral oximetry Nasal irritation: (Combined participant and investigator reported nasal symptoms will be collected from all patients) Sedation: (The University of Michigan Sedation Scale (Malviya et al, Anesthesiology 2004)) Unsolicited adverse events (incl CNS AE's)
To evaluate the analgesic effect of CT001 in pediatric participants with moderate to severe pain in an acute care setting	Number and proportion (%) of participants that respond to the treatment relative to baseline (i.e. reduction in pain score to 4 or below) at 15 min post IMP administration.  Number and proportion (%) of participants that respond to the treatment relative to baseline (i.e. reduction in pain score to 4 or below) within 30 min post IMP administration.	Pain intensity score: For age group $\geq$ 1 year to $<$ 5 years FLACC score (assessed by site staff). For age group $\geq$ 5 years up to 9 years visual analogue scale modified with Wong-Baker faces For age group 9 to $<$ 18 years Numerical Rating Scale (NRS) 0-10.

Secondary Objectives	Endpoints	Assessments
To assess medication errors in pediatric participants with moderate to severe pain in an acute care setting	Number of medication errors	Type of medication errors (will be obtained via feedback from site staff that administer the IMP)

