### **3.1 Inclusion Criteria**

To participate in the study, and prior to performing any study-related procedures, the following inclusion criteria must all be met:

1. Participant aged 1 to <18 years.
2. Attending an ED following an injury.
3. A pain intensity score corresponding to moderate or severe pain, as assessed by age relevant scales:
  - Age group ≥9 to <18 years: pain score 5 to 10 using the Numerical Rating Scale (NRS); self-reporting by the participant.
  - Age group ≥5 to <9 years: pain score 6 to 10 using the Wong-Baker FACES scale; self-reporting by the participant.
  - Age group ≥1 to <5 years: pain score 5 to 10 using the FLACC pain scale; assessed by site staff.
4. Evidence of signed and dated informed consent form, indicating that the participant and/or parent/ guardian (if participant younger than 16 years) has been informed of and has fully understood all pertinent aspects of the study as required for the age of the child in accordance with local legislation.

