### 4.3.2 Pain intensity assessments

The pain resulting from injury causing the emergency visit will be quantified. The participant will be introduced to the age-appropriate pain scale and overall pain will be assessed, with no distinction made between spontaneous pain and any procedural pain.

Immediately prior to administration of the IMP (baseline), the pain intensity will be rated using the applicable tool (see below). Subsequent pain assessments will be performed at 10, 15, 20, 30, 45, and 60 min post IMP administration. If a second dose of IMP is administered after 10-15 min, the pain assessment schedule will be reset, and pain will be measured at 10, 15, 20, 30, 45, and 60 min after the second dose of IMP, or until additional analgesics or procedures needs to be initiated.

Unscheduled pain intensity scores will be measured and recorded during any potentially painful intervention (e.g. during the application of a plaster cast for a fracture), prior to rescue medication or prior to premature study withdrawal.

Age-appropriate pain intensity assessment tools will be used:

**Age ≥9 years:** The Numerical Rating Scale (NRS) will be used. The NRS scales consists of a Likert scale, anchored with numbers 0-10, with 0 marked "No pain" and the right end (10) marked "Worst pain imaginable". The patient will state the number representing their current level of pain, and the study staff will circle the applicable number on the CRF page (see [Appendix A](#)).

**Age ≥5 to <9 years:** The visual analogue scale modified with six faces developed by Wong-Baker (Wong-Baker FACES pain rating scale) will be used. Numerical values (0, 2, 4, 6, 8, 10) are listed for each face (Wong et al, 2001, see [Appendix B](#)).

**Age 1 to <5 years:** The study investigator will provide an assessment of pain, using the FLACC scale (Merkel et al, 1997, see [Appendix C](#)).

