#### 6.1.2 Secondary efficacy variable

To evaluate additional analgesic effect of CT001 in pediatric participants with moderate to severe pain in an acute care setting

- Maximum change from baseline in pain intensity within 30 min post IMP administration.
- Number and proportion of participants that achieve a 30% reduction in pain intensity relative to baseline within 30 min post IMP.
- Change from baseline in pain intensity at 10, 15, 20, 30, 45 and 60 min post IMP.
- Derived variables such as area under curve (AUC), peak change in pain intensity from baseline, and duration of effect will be calculated from the recorded pain assessments.

To evaluate the need for supplemental analgesic medication during the study period

- Number and proportion of children receiving additional analgesics, as assessed by timepoint.

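### The only primary efficacy proportion with a planned confidence interval counts the best of several readings, so it is more lenient than the fixed-time rate used to plan the trial

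*Combined protocol and SAP*

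**What the plan says.** There are two primary efficacy proportions, listed separately in the Protocol Outline: a score of 4 or below at 15 min, and a score of 4 or below within 30 min. For the second, section 6.1.1 accepts a qualifying score "at any timepoint during 30 min post IMP". It schedules pain scores "at 10, 15, 20, 30, 45, 60 min post first IMP dose", so four readings (10, 15, 20 and 30 min) fall in the window.

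That number is not fixed:
- After a second dose, section 4.3.2 says "the pain assessment schedule will be reset".
- Scoring continues for 60 min "or until additional analgesics or procedures needs to be initiated", and section 4.3.7 leaves post-rescue scores out of the efficacy analyses.
- Section 4.2 adds unscheduled scores.

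Entry under section 3.1 starts at 5 on the NRS and FLACC and at 6 on Wong-Baker. The study has no control arm.

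Section 7.4.1 makes the primary efficacy analysis descriptive. It plans a 95% confidence interval for the within-30-min proportion, by age group and overall, and none for the 15-min proportion. (Its interval sentence speaks of a reduction *of* 4 or less; I read this as a reduction *to* 4 or below, as in the sentence before it.)

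Section 7.1 gives the planning basis: "A previous study reported a responder rate of 71.6" per cent, for a score of 3 or below at 30 min, with 113 patients to show a rate above 60%.

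Section 6.1.2 has as a secondary endpoint: "Number and proportion of participants that achieve a 30% reduction in pain intensity relative to baseline within 30 min post IMP".

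**The concern.** A best-of-several rule rewards variability. Each extra reading gives a child another chance to fall to 4 or below through measurement error or natural fluctuation, and one such score settles the matter even if the others are higher. Without a control arm, the trial cannot show how much of the observed rate arises this way.

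The proportion most exposed to this is the one that will carry the interval. Readers will naturally set that interval beside the 60% and 71.6% in section 7.1. The 71.6% comes from a definition that is stricter twice over: a lower cut-off and a single fixed time. No planned row matches that definition, so the result could look better against its planning figures than a like-for-like comparison would.

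**Working it through.** **1. The plan's own figure.** Inputs from section 7.1: p0 = 0.60, p1 = 0.716, one-sided alpha 0.05, power 80%.

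Score formula: n = [(1.645·√(0.60·0.40) + 0.842·√(0.716·0.284)) / 0.116]² = 104.4, so 105.

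With continuity correction: (104.4/4)·[1 + √(1 + 2/(104.4·0.116))]² = 112.9, so 113, as stated.

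Exact binomial at n = 113, claiming success at 77 or more responders: size 0.046, power 0.822. Dropout: 113/0.75 = 150.7, against the stated 150. The figure reproduces with 71.6% as the alternative, so the fixed-time rate enters the sample size directly.

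**2. Direction, without assumptions.** A child at 4 or below at 15 min or at 30 min is by definition at 4 or below at some time in the window. With complete readings, the within-30-min rate therefore cannot be lower than either fixed-time rate.

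**3. How many readings count.** Without a second dose: 10, 15, 20 and 30 min, so four. With a second dose at 15 min and the schedule restarted, readings fall at 10, 15, 25, 30, 35 and 45 min from the first dose. Four of these lie within 30 min of the first dose; six count if the window runs to 30 min after the second. Rescue or a procedure can reduce the number. The text does not say which dose starts the 30 min.

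**4. Noise only, no drug effect.** Assumptions of mine: constant true pain, normal error with SD 1, scores rounded to whole numbers, within-child error correlation 0 or 0.5.
- One reading, true pain 5: P(score ≤ 4) = Φ(4.5 − 5) = 0.309.
- Any of four, independent: 1 − 0.691⁴ = 0.77.

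| True pain | One reading | Any of four (corr. 0.5 to 0) | Two consecutive |
|---|---|---|---|
| 5 | 31% | 60–77% | 23–28% |
| 6 | 7% | 18–24% | 1–4% |
| Uniform 5–10 | 6% | 13–17% | 4–5% |

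**5. Whole trial.** Further assumptions: 40% of children on Wong-Baker with two-point steps (the 50 flexible places in section 5.4 following the 20/40/40 ratio), SD 1 to 2, correlation 0 to 0.8.

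| Baseline mix | One reading | Any of four |
|---|---|---|
| Most at 5–6 | 12–23% | 20–58% |
| Uniform | 6–13% | 10–35% |
| Most at 7 or above | 2–8% | 4–24% |

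At SD 0.5 the any-of-four range is about 1–13%. For SD 1 to 2, any-of-four raises the noise-only rate about 1.6 to 3 times.

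**6. With a drug effect.** Suppose the true proportion at 4 or below is 50% at each of the four times, with a common latent normal correlation ρ. Any-of-four = 1 − ∫φ(u)·Φ(−u√ρ/√(1−ρ))⁴du, which gives 80% at ρ = 0.5, 69% at 0.8 and 63% at 0.9.

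In exact 95% intervals at n = 150: 75/150 gives 42–58%, while 103/150 (69%) gives 61–76%. At n = 113, 78/113 (69%) gives 60–77%, with a lower limit of 59.6%. A product below 60% at a fixed time could thus show an interval at or above 60% on the planned endpoint.

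**The case against.** Much can be said for the plan as written.

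- **A fixed-time primary endpoint exists.** The 15-min proportion is reported beside the any-time rate, and its interval can be computed from the count. This stands. The gap is an unplanned interval and a missing 30-min proportion, not a missing fixed-time endpoint.
- **The analysis is descriptive.** Sections 7.4 and 7.4.1 contain no test and no success rule against 60%. A reader might infer that 60% was derived from the fixed-time rate; section 7.1 does not say so. What remains is that 71.6% is the only outside rate cited and that the sample size is framed as showing a rate above 60%.
- **Supportive analyses exist.** Section 7.4.2 reports change from baseline at each time and 30% responders by timepoint. Section 6.1.2 lists AUC and duration of effect, the latter undefined. A separate, more detailed SAP is to be signed before database lock. These help, but none of the listed analyses gives a proportion at 4 or below, or 3 or below, at 30 min.
- **The one-point response is narrow.** A reader might infer that any child can qualify on a trivial change. A 5-to-4 change (20%) needs an NRS or FLACC child with baseline exactly 5 and best score exactly 4. From a baseline of 6, reaching 4 is already 2/6 = 33%. On Wong-Baker the smallest qualifying step from the entry score is 6 to 4.
- **The 77% is an extreme.** A reader might infer that noise alone could produce the planning rate. The figure requires true pain of exactly 5 and independent errors. No whole-trial scenario I examined reached 60%.

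**Conclusion.** The point holds as one of leniency and comparability. The within-30-min endpoint is a best-of-several rate without confirmation or control. It is the only primary efficacy proportion with a planned interval, and no planned row matches the definition behind the 71.6% planning rate. The direction is certain where readings are complete.

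The size depends on noise SD, correlation and baseline mix, none of which the documents give. For children near the threshold the inflation can be large (31% to 60–77% at true pain 5). With pain spread evenly over 5–10 it is modest in absolute terms (6% to 13–17%). With a true fixed-time rate of 50%, the headline would be about 69% at correlation 0.8 and 80% at 0.5. That calculation assumes the same rate at all four times; a slower onset would change it.

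The documents do not support saying that noise alone would deliver 60% responders across the trial, or that the plan formally tests against 60%. This is a worthwhile reporting change and does not invalidate the endpoint.

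**What to change.** Keep both primary endpoints. In section 7.4.1, and in the SAP before database lock:

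1. Add a 95% confidence interval for the 15-min proportion, by age group and overall.
2. Report, with 95% confidence intervals, the proportion at 4 or below at the fixed 30-min reading and, for comparison with the planning rate, the proportion at 3 or below. State the denominator, how children without a 30-min score are handled (section 7.3 plans no imputation), and which dose starts the clock.
3. As a supportive row, report the proportion at 4 or below on two consecutive scheduled scores within 30 min, with a rule for children whose readings stop early. This row fails a child who first reaches 4 at 30 min, so it should not lead.
4. State that the within-30-min rate is a best-of-several rate, not directly comparable with the 60% and 71.6% planning figures.

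A joint row requiring both 4 or below and a 30% reduction is not needed: it differs from the headline only for children with baseline 5 and best score 4. Nor is a rule that all rows must agree, which would add an undefined success criterion to a descriptive study.

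Cost: a few extra table rows from data already scheduled. The downside is that the supportive rates will be lower than the headline rate.
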